Study Day	Screening	Cycle 1							Cycle 2					Cycles 3-15 (a, b)		Even-Numbered Cycles (C16+ beyond) (a, b)		Odd-Numbered Cycles (C17+ beyond) (a, b)		EOT (c)	SFU	Long-Term Follow-Up
		1	2	4*	8	11*	15	22	1	8*	15	22*	1	22	1	22	1	22	30 d after last dose			
Window (Days)				±1	±2	±1	±2	±2	±2	±2	±2	±2	±3	±3	±3	±3	±3	±3		±7	±7	
Informed consent	X																					
Randomization	X (d)																					
Medical history	X																					
Demographics	X																					
Physical examination (e)	X	X			X		X	X	X		X		X				X		X	X		
Vital signs; weight; height (f)	X	X			X		X	X	X		X		X				X		X	X		
ECOG performance status	X	X			X		X	X	X		X		X				X		X	X		
ECG (g)	X	X (h)	X				X		X (h)		X		X				X		X			
Hematology (i)	X	X		X*	X	X*	X	X	X	X*	X	X*	X		X		X		X	X		
Clinical chemistry (i)	X	X		X*	X	X*	X	X	X	X*	X	X*	X		X		X		X	X		
Serum tryptase (j)	X	X	X		X		X	X	X		X		X		X				X			

Table 1: Schedule of Assessments and Procedures

	Screening	Cycle 1							Cycle 2					Cycles 3-15 (a, b)		Even-Numbered Cycles (C16+ beyond) (a, b)		Odd-Numbered Cycles (C17+ beyond) (a, b)		EOT (c)	SFU	Long-Term Follow-Up
		1	2	4*	8	11*	15	22	1	8*	15	22*	1	22	1	22	1	22	30 d after last dose			
Study Day	-42 to -1	1	2	4*	8	11*	15	22	1	8*	15	22*	1	22	1	22	1	22		±7	±7	
Window (Days)				±1	±2	±1	±2	±2	±2	±2	±2	±2	±3	±3	±3	±3	±3	±3		±7	±7	
Blood samples for mutational analysis (KIT D816V burden)	X										X		X		X				X			
Coagulation tests	X	X																	X			
Virus serology	X (k)																					
Pregnancy test (l)	X	X							X				X		X		X		X	X		
Blood sample for PD	Refer to Table 2 Schedule of Pharmacokinetic, Pharmacodynamic, and Biomarker Assessments.																					
Blood sample for PK	Refer to Table 2 Schedule of Pharmacokinetic, Pharmacodynamic, and Biomarker Assessments.																					
Bone marrow aspirate, biopsy, and PBS	Refer to Table 3 Schedule of Response Assessments.																					
Photography	Refer to Table 3 Schedule of Response Assessments.																					

Table 1: Schedule of Assessments and Procedures

	Screening	Cycle 1							Cycle 2					Cycles 3-15 (a, b)		Even-Numbered Cycles (C16+ beyond) (a, b)		Odd-Numbered Cycles (C17+ beyond) (a, b)		EOT (c)	SFU	Long-Term Follow-Up
Study Day	-42 to -1	1	2	4*	8	11*	15	22	1	8*	15	22*	1	22	1	22	1	22			30 d after last dose	Every 3 months after SFU
Window (Days)				±1	±2	±1	±2	±2	±2	±2	±2	±2	±3	±3	±3	±3	±3	±3			±7	±7

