Radiological Evaluations - MRI/CT abdomen/pelvis - Skeletal imaging (as appropriate)	Refer to Table 3 Schedule of Response Assessments.																					
Spleen palpation	Refer to Table 3 Schedule of Response Assessments.																					
QOL assessments (m)		X							X				X				X		X			
MAS (n)	X							X				X		X				X	X			
Bezuclastinib administration (o)	Daily through Cycle (a)																					
Study drug diary (p)		X							X				X (a)		X (a)		X (a)					
Overall response assessment	Refer to Table 3 Schedule of Response Assessments																					
AE monitoring (q)	X	X																				

Table 1: Schedule of Assessments and Procedures

	Screening	Cycle 1							Cycle 2				Cycles 3-15 (a, b)		Even-Numbered Cycles (C16+ beyond) (a, b)		Odd-Numbered Cycles (C17+ beyond) (a, b)		EOT (c)	SFU	Long-Term Follow-Up
Study Day	-42 to -1	1	2	4*	8	11*	15	22	1	8*	15	22*	1	22	1	22	1	22		30 d after last dose	Every 3 months after SFU
Window (Days)				±1	±2	±1	±2	±2	±2	±2	±2	±2	±3	±3	±3	±3	±3	±3		±7	±7
Concomitant medications (q)	X	X																			
Survival status (r)																					X
Disease status (s)																					X

Abbreviations: AE=adverse event, C=Cycle, CT=computed tomography, D/d=day, ECG=electrocardiogram, ECOG=Eastern Cooperative Oncology Group, eCRF=electronic case report form, EOT=end of treatment, HCV=hepatitis C virus, ICF=informed consent form, IWG-MRT-ECNM=International Working Group-Myeloproliferative Neoplasms Research and Treatment European Competence Network on Mastocytosis, MAS=Mastocytosis Activity Score, MRI=magnetic resonance imaging, PBS=peripheral blood smear, PE=physical examination, PK=pharmacokinetic, QOL=quality of life, SAE=serious adverse event, SFU=Safety Follow-up, TEAE=treatment-emergent adverse event.

One cycle = 28 days.

Standard of care assessments or procedures that may confirm study eligibility requirements may be performed prior to a subject signing the ICF.

On-treatment assessments and sample collections will be performed prior to dosing with study drug and, as applicable, prior to ECG for scheduled visits involving study drug administration and/or ECGs, unless otherwise noted. Additional assessments to evaluate subject safety and efficacy may be performed at unscheduled visits and will be recorded in the eCRFs.

* Additional hematology and chemistry assessments to be performed for subjects in Part 1 and Part 2 Stage 1 only.

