- (n) The MAS will be completed where appropriate translations are available at Screening on D -42 (\pm 5 days) through D -35 (\pm 5 days). Thereafter, the MAS will be completed on Days 22-28 of each 28-day cycle through C15 and on Days 22-28 of odd-numbered cycles at C17 and beyond. The MAS must be completed at EOT and continuing for 7 days total unless an MAS was completed within the previous 14 days. The time window for starting the MAS is \pm 2 days.
- (o) Study drug bezuclastinib will be dispensed to the subject on Day 1 of each cycle for daily at-home administration. Treatment will be continuous; there will be no gaps between cycles. On days of a scheduled clinic visit, study drug will be administered at the clinic after visit procedures and assessments are performed.
- (p) A Study Drug Diary will be dispensed to the subject at the start of each cycle. Beginning at Cycle 15, subjects will be provided with diaries for use over 2 cycles. Subjects bring their diary with them to each study visit. Diary information will be reviewed and/or collected by the site during study visits.
- (q) From the signing of the ICF until the start of study treatment (C1D1), only SAEs or AEs related to on-protocol procedures will be collected. TEAEs will be collected from the start of study treatment until 30 days after the last dose of study drug. All medications will be recorded at Screening and collected through 30 days after the last dose of bezuclastinib. Any SAEs considered to have at least a possible relationship to the study drug and discovered by the Investigator at any time period after EOT should be reported.
- (r) Survival follow-up may be done via phone (with subject or referring physician).
- (s) Includes the recording of new anticancer therapy (therapy type, start and stop dates, and response to treatment).

Table 2: Schedule of Pharmacokinetics, Pharmacodynamics, and Biomarker Assessments

		Screening	Cycle 1			Cycle 2			Cycles 3-15 (a)	Odd-Numbered Cycles (C17 + beyond) (a)	EOT
Study Day		-42 to -1	1	2	15	1	2	15	1	1	
Blood sample for PGx (b)		X (b)									
Buccal swab for TPSAB1 gene (HAT) (c)		X (c)									
Blood sample for bezuclastinib PK	Predose: -30 min		X	X	X	X	X	X	X	X	
	Postdose: 1 h (± 5 min), 3 h (± 15 min), 5 h (± 15 min), 8 h (± 30 min)		X (d)			X (d)					
	Any time during Study Visit										X

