6.15.6. Survival and Disease Status

Subjects who discontinue study treatment but remain on study in long-term follow-up will be contacted as specified in the Schedule of Assessments ([Table 1](#)) for survival and disease status. Subjects will be followed for survival for at least 2 years after study drug discontinuation until death, withdrawal of consent, lost to follow-up, Investigator decision, enrollment in another therapeutic study, or the end of the study. New anticancer therapies must be recorded during this period including therapy type, start and stop dates, and response to treatment.

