6.16. SAFETY ASSESSMENTS

6.16.1. Adverse Events

From the signing of the study informed consent form until the first dose of bezuclastinib, only SAEs and AEs considered related to on-protocol procedures will be collected. All AEs that are ongoing at the time of the first dose of bezuclastinib will be recorded as medical history. All new AEs will be collected from the first dose of bezuclastinib until 30 days after the last dose of study drug.

AEs will be reported as described in [Section 7.2](#).

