7.2. PROCEDURES FOR RECORDING AND REPORTING ADVERSE EVENTS

7.2.1. Adverse Event Recording

Each subject must be carefully monitored for the development of any AEs. This information should be obtained in the form of non-leading questions (eg, “How are you feeling?”) and from signs and symptoms detected during each assessment, observations of study personnel, and spontaneous reports from subjects.

After the ICF is signed, site personnel will note any change in the condition(s) and the occurrence and nature of any AEs. From the signing of the study informed consent form until the first dose of bezuclastinib, only SAEs and AEs considered related to on-protocol procedures will be collected. TEAEs will be recorded from the start of study treatment until 30 days after the last dose of study drug.

All AEs (serious and non-serious) will be monitored until resolved, stabilized, or returned to baseline status during study participation.

After receipt of any study drug, all AEs spontaneously reported by the subject and/or in response to an open question from the study personnel or revealed by observation will be recorded via eCRF.

Laboratory abnormalities or other abnormal assessments (eg, physical examination findings, vital signs, ECGs) should only be recorded as AEs if clinically significant (ie, requiring medical or surgical intervention); abnormalities that lead to investigational therapy discontinuation, delay, or interruption; or abnormalities associated with clinical signs or symptoms.

Whenever possible, the clinical diagnosis, rather than the laboratory result or signs and symptoms, should be reported by the Investigator (eg, anemia vs decreased hematocrit) as 1 comprehensive event.

If a constellation of signs and/or symptoms cannot be medically characterized as a single diagnosis or syndrome at the time of reporting, each individual event should be recorded on the eCRF. If a diagnosis is subsequently established, all previously reported AEs should be replaced based on the single diagnosis.

The AE term should be reported in standard medical terminology when possible.

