7.2.4. Serious Adverse Event Reporting

All SAEs that occur following the signing of informed consent are to be reported within 24 hours from the point in time when the Investigator becomes aware of the SAE. This 24-hour notification requirement refers to the initial SAE information and all follow-up SAE information. All SAEs must be reported whether or not they are considered causally related to the investigational product. SAE forms will be provided to each clinical site. The information collected will include subject number, a narrative description of the event and an assessment by

the Investigator as to the severity of the event and relatedness to bezuclastinib. Follow-up information on the SAE may be requested by the Sponsor or its designee.

Any SAE that is ongoing when the subject completes or discontinues the study (with the exception of subjects who withdraw consent) will be followed by the Investigator until the event has resolved, stabilized, or returned to baseline status.

Contact information for reporting SAEs is provided in the Operations Manual.

If an Investigator becomes aware of an SAE after the subject's participation in the study has ended that is considered related to study treatment, the Investigator should report the SAEs to the Sponsor.

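### The ±7-day window lets the Safety Follow-up fall on Day 23, so up to 7 days of the 30-day TEAE period may have no scheduled active ascertainment

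*Protocol*

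**What the plan says.** Three places in the protocol end collection on the same day. Table 1, footnote (q): "TEAEs will be collected from the start of study treatment until 30 days after the last dose of study drug". Section 6.16.1: "All new AEs will be collected from the first dose of bezuclastinib until 30 days after the last dose of study drug". Section 7.2.1: "TEAEs will be recorded from the start of study treatment until 30 days after the last dose of study drug". Concomitant medications run to the same day (footnote (q) and Section 6.16.2).

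The visit that serves this period is the SFU. Table 1 places it at "30 d after last dose", and the window row gives ±7 days. Haematology and clinical chemistry are scheduled there for the last time.

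After the SFU comes long-term follow-up, "Every 3 months after SFU", also ±7 days. Section 6.15.6 says that these subjects "will be contacted as specified in the Schedule of Assessments". The items that the schedule gives for this period are survival status and disease status, including new anticancer therapy. Footnote (r) allows the survival contact to be a phone call to the subject or the referring physician.

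The protocol also has reporting rules that do not depend on a visit. Footnote (q) asks for reporting of "Any SAEs considered to have at least a possible relationship to the study drug and discovered by the Investigator at any time period after EOT". Section 7.2.4 states that "All SAEs that occur following the signing of informed consent are to be reported within 24 hours" of the investigator becoming aware, whatever the causality. Section 7.2.5 applies the same timelines to AEs of clinical interest, which Section 7.1.3 defines as Grade 3 or higher QTc prolongation, hepatic events and bleeding events.

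**The concern.** The collection period and the visit that closes it do not line up. A symmetric window around Day 30 allows the last scheduled safety assessment to come before the period ends, and nothing scheduled afterwards makes up the difference. How long a subject is actively asked about adverse events then depends on when the visit happened to be booked.

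Section 8.9 makes TEAE incidence the primary safety endpoint, so ascertainment should be the same for every subject over the stated period. Section 7.2.1 relies on non-leading questions and on signs found at each assessment, and both need an assessment to take place. Section 1.4 lists symptom-free liver enzyme rises and haematological toxicity among the important potential risks. A subject cannot volunteer a laboratory change that causes no symptoms. The analysis plan cannot repair this later, because it cannot recover events that nobody asked about.

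**Working it through.** The check is date arithmetic. No sample size, power or alpha figure is involved.

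**Inputs**
- End of TEAE collection: Day 30 after last dose (Table 1 footnote (q); Sections 6.16.1 and 7.2.1).
- SFU: Day 30, window ±7 days (Table 1).
- Next scheduled contact: 3 months after SFU, ±7 days (Table 1), with 3 months taken as 91 days (assumption).
- Cycle length: 28 days (protocol Synopsis).

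**1. Permitted SFU days.** Earliest 30 − 7 = Day 23. Latest 30 + 7 = Day 37.

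**2. Largest gap.** 30 − 23 = 7 days (Days 24 to 30). As a share of the post-treatment period, 7/30 = 23%.

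**3. Next scheduled contact after a Day 23 visit.** 23 + 91 = Day 114, or Days 107 to 121 with the ±7-day window. AE collection is not among the items listed for it.

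**4. Average gap.** The protocol does not say how visits spread over the window, so only a range can be given. If every visit falls on Day 30 or later, the gap is 0. If every visit falls on Day 23, it is 7 days. If visits were spread evenly over the 15 permitted days (assumption), 7/15 = 47% would fall before Day 30, and the mean gap over all subjects would be (1 + 2 + … + 7)/15 = 28/15 = 1.9 days, or 1.87/30 = 6% of the post-treatment period.

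**5. Against the whole TEAE period.** TEAEs count from the first dose, so the gap is also shown against treatment time plus 30 days. The treatment durations are assumptions.

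| Cycles treated | TEAE period | Largest gap | Mean gap (even spread) |
|---|---|---|---|
| 2 | 2 × 28 + 30 = 86 days | 7/86 = 8.1% | 1.87/86 = 2.2% |
| 6 | 6 × 28 + 30 = 198 days | 7/198 = 3.5% | 1.87/198 = 0.9% |
| 13 | 13 × 28 + 30 = 394 days | 7/394 = 1.8% | 1.87/394 = 0.5% |

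**6. After the change.** With a 0/+7 window the earliest SFU is Day 30, and the largest gap is 30 − 30 = 0 days. A required Day 30 contact for anyone seen earlier gives the same result.

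**The case against.** The strongest answer is that the duty to collect is set by the calendar, not by the visit. All three places run to Day 30 wherever the SFU falls. Section 7.2.1 counts spontaneous reports as a source, the notes to Table 1 allow safety assessments at unscheduled visits and have them recorded, and the remote-visit section allows telemedicine for emerging events. This stands, and it means the protocol does not contradict itself. But none of these routes is required after the SFU, and reporting on awareness presupposes a contact that creates the awareness.

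A reader might infer that unrelated SAEs in Days 24 to 30 drop out, because footnote (q) speaks only of possibly related SAEs after EOT. The documents do not support that. Section 7.2.4 covers all SAEs regardless of causality, and limits this to related events only once participation has ended. Section 6.15.6 treats subjects in long-term follow-up as still on study.

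A reader might also infer that events soon after stopping are lost selectively. They are not: Days 1 to 23 are covered even by the earliest SFU, and nothing links early visits to stopping for toxicity. With the half-life of about 2 to 3 days given in Appendix K, at least 23/3 = 7.7 half-lives have passed by Day 23, leaving under 0.5% of the drug. That makes drug-caused events in the gap less likely. It does not take them out of the TEAE definition, which runs to Day 30 regardless of cause.

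Two further limits apply. Section 7.2.1 records laboratory abnormalities as AEs only if they are clinically significant, change treatment or come with signs or symptoms, so few silent changes this late would count as TEAEs. And in the text available for this review, the AE-monitoring row of Table 1 is a merged cell whose right-hand end cannot be read. That the SFU is the last scheduled AE contact is inferred from footnote (q) and from what long-term follow-up lists.

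**Conclusion.** The point holds as a minor scheduling mismatch. A compliant SFU can come up to 7 days before TEAE collection ends, and no later scheduled contact lists AE, concomitant medication or safety laboratory collection. What may be missing is active ascertainment, chiefly of non-serious events.

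It would go too far to say that the week goes unobserved, or that TEAE incidence is understated by a known amount. Seven days is the permitted maximum, and the 47% and 1.9-day figures rest entirely on an assumed even spread of visits. Incidence also counts a subject once per term, so it changes only if a new non-serious event first arises in the gap and is never reported. The expected effect is small. The response rate analysis, its power and its error rate are untouched.

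**What to change.** In Table 1, change the SFU window from ±7 to 0/+7 days, so that the visit falls on Days 30 to 37. Alternatively, keep ±7 and add to footnote (q) that anyone seen before Day 30 is contacted on Day 30, for example by phone, for adverse events and concomitant medications.

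The first option is one table cell. It costs sites some scheduling flexibility and moves the SFU laboratory tests up to a week past Day 30. The second leaves the visit and its tests where they are and costs one call per subject seen early, but a call would not pick up silent laboratory changes. Neither touches dosing, treatment rules, endpoints or the analysis.

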ECOG	Eastern Cooperative Oncology Group
eCRF	electronic case report form
GCP	Good Clinical Practice
G-CSF	granulocyte colony-stimulating factor
GIST	gastrointestinal stromal tumor
GLP	Good Laboratory Practice
HCV	hepatitis C virus
hERG	human ether-à-go-go related gene
HSCT	hematopoietic stem cell transplantation
IB	Investigator's Brochure
IC ₅₀	half-maximal inhibitory concentration
ICF	informed consent form
ICH	International Council on Harmonisation
IDMC	Independent Data Monitoring Committee

Abbreviation	Definition
IEC	Independent Ethics Committee
IRB	Institutional Review Board
IRT	Interactive Response Technology
ITT	intent to treat
IWG-MRT-ECNM	International Working Group-Myeloproliferative Neoplasms Research and Treatment European Competence Network on Mastocytosis
MAS	Mastocytosis Activity Score
MCL	mast cell leukemia
MC-QoL	Mastocytosis Quality of Life Questionnaire
MedDRA	Medical Dictionary for Regulatory Activities
MRI	magnetic resonance imaging
MTD	maximum tolerated dose
NCCN	National Comprehensive Cancer Network
NCI	National Cancer Institute
NICE	National Institute for Health and Care Excellence
NOAEL	no observed adverse effect level
ORR	overall response rate
OS	overall survival
PBS	peripheral blood smear
PFS	progression-free survival
PGIC	Patient Global Impression of Change
PGIS	Patient Global Impression of Severity
PI	Principal Investigator
PK	pharmacokinetic
PPR	pure pathologic response
PR	partial response
QD	once daily
SAE	serious adverse event
SAP	statistical analysis plan
SM	systemic mastocytosis
SM-AHN	systemic mastocytosis with an associated hematologic neoplasm
SSC	Study Steering Committee
SUSAR	suspected unexpected serious adverse reaction
TEAE	treatment-emergent adverse event

Abbreviation	Definition
TKI	tyrosine kinase inhibitor
TTR	time to response
ULN	upper limit of normal
VAF	variant allele frequency
WHO	World Health Organization
WOCBP	women of childbearing potential

1. INTRODUCTION

1.1. MASTOCYTOSIS

Mastocytosis is a group of rare disorders characterized by an abnormal clonal proliferation of mast cells in the bone marrow, skin, gastrointestinal tract, and other organs (Gilreath et al, 2019; Gotlib et al, 2018; Pardanani, 2019). The disorder has been characterized by the 2016 World Health Organization (WHO) classification into 2 distinct categories, cutaneous mastocytosis and systemic mastocytosis (SM) (Arber et al, 2016). Systemic mastocytosis, characterized by mast cell infiltration of 1 or more extracutaneous organs (with or without skin involvement), encompasses a spectrum of diagnoses ranging from non-advanced to advanced disease.

Advanced systemic mastocytosis (AdvSM), an aggressive and life-threatening form of the disease contains 3 subtypes: aggressive systemic mastocytosis (ASM), systemic mastocytosis with an associated hematologic neoplasm (SM-AHN), and mast cell leukemia (MCL) (NCCN Systemic Mastocytosis, Version 2.2019; Pardanani, 2019; Shomali et al, 2018). These conditions are described in detail in the 2016 WHO classification of myeloid neoplasms (Arber et al, 2016).

SM is considered an orphan disease in the United States and European Union. AdvSM comprises 10% of the general SM population. WHO diagnostic criteria for SM include 1 major diagnostic criterion (multifocal, dense infiltrates of mast cells [≥ 15 mast cells in aggregates] detected in the biopsy sections of bone marrow and/or other extracutaneous organs) and 4 minor diagnostic criteria (the presence of atypical mast cells in lesional tissues, the presence of *KIT* D816V mutation, the aberrant expression of CD25 with or without CD2 on neoplastic mast cells, and a persistently elevated serum tryptase level [>20 ng/mL; unless there is associated clonal myeloid disorder, in which case this criterion is not valid]). A diagnosis requires 1 major and 1 minor criterion or at least 3 minor criteria (Gotlib et al, 2018; Gotlib et al, 2013; Pardanani, 2019). The molecular pathogenesis of SM is driven by mutations in the *KIT* gene leading to constant proliferation of mast cells, with 95% of patients with systemic mastocytosis having a mutation on exon 17, D816V (Garcia-Montero et al, 2006; Jara-Acevedo et al, 2015; Vaes et al, 2017).

Clinically, patients with SM present with a variety of symptoms depending on the subtype of disease and presence of B- and C-findings. B-findings refer to organ involvement without organ dysfunction and C-findings refer to organ involvement with organ dysfunction (Magliacane et al, 2014). SM symptoms are related to mediator release and include skin rashes, diarrhea, vomiting, abdominal pain, fatigue, headache, cognitive impairment, anxiety and depression, and anaphylaxis (Gotlib et al, 2018; Jennings et al, 2014). Other clinical findings arise from (noncutaneous) organ filtration such as cytopenias, hepatomegaly with liver dysfunction, splenomegaly, malabsorption and weight loss, and skeletal involvement (Gotlib et al, 2018; Pardanani, 2019; Rossignol et al, 2019). The symptoms of SM can be severe and unpredictable and negatively affect quality of life (Chang et al, 2000; Emanuel et al, 2012; Gotlib et al, 2018; Jennings et al, 2014; Ustun et al, 2016).

AdvSM is a serious and life-threatening disease. Depending on the subtype of AdvSM, the median overall survival can range from 2 months in patients with MCL to 41 months in patients with ASM (Gotlib et al, 2018; NCCN Systemic Mastocytosis, Version 2.2019; Pardanani, 2019; Rossignol et al, 2019; Shomali et al, 2018).

